4.2.2.1 Multiplicity Adjustment

The primary analysis of the primary variable and key secondary analysis of the key secondary variable will consist of 2 hypothesis testing of treatment comparisons. Multiplicity adjustment will be applied to control the Type-I error rate by conducting the hypothesis testing in the following hierarchical order [CPMP (2002)]:

1. fingolimod vs. IFN β -1a testing treatment difference for ARR;
2. fingolimod vs. IFN β -1a testing treatment difference for annualized rate of the number of new/newly enlarged T2 lesions;

Each hypothesis testing will be performed at a significant level of 0.05. However, the lower-ranked testing will be performed only when the higher-ranked testing preceding it is statistically significant at 0.05.

4.2.2.2 New/newly enlarged T2 lesions

The key secondary variable is the annualized rate of the number of new/newly enlarged T2 lesions (n/neT2) from baseline to end of the core phase, with a duration up to 24 months.

The null hypothesis for the key secondary analysis states that: there is no reduction in then/neT2 lesion rate in subjects treated with fingolimod compared to subjects treated with

IFN β -1a, while the alternative hypothesis states there is a reduction in the n/neT2 lesion rate, in fingolimod treated subjects.

4.2.2.2.1 Key secondary analysis

The test of the null hypothesis will be based on a negative binomial regression model adjusted for treatment, number of T2 lesions at baseline, pubertal status (the stratification factor in IVRS), and region. The natural log of time in study for each patient will be used as the offset.

For the key secondary analysis, there will be no imputations for missing data. The response variable for this analysis is the cumulative number of n/neT2 lesions up to Month 24 (i.e., Month 0 to EOS), for each subject. The quadratic variance estimate will be used and the natural log of time (in years) from first dose of study treatment to the last available T2 MRI assessment date for subject will be used as the offset to account for the varying lengths of each subject's time in the study.

The above null hypothesis will be rejected if the observed p-value for treatment comparison (based on the n/neT2 rate ratio) is less than the significance level of 0.05. Model-based estimates (LSmean estimated with the OM option) of the annualized rate of the number of n/neT2 lesions from baseline to end of the core phase, with a duration up to 24 months and their 95% confidence intervals, estimate of the n/neT2 rate ratio (i.e., relative treatment effect) and its 95% confidence intervals and p-value for comparing fingolimod vs. IFN β -1a i.m. will be provided.

The number of n/neT2 relative to baseline and the number of n/neT2 relative to previous visit will also be summarized (mean, standard deviation, median, minimum and maximum) by visit.

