A neuroradiologist will be responsible for:

- Previewing each MRI scan performed for the study patients
- Contacting the Primary Treating Physician in case of unexpected findings detected on the MRI scan

Ophthalmologist

- The Ophthalmologist will perform the ophthalmic examinations as per protocol

Pulmonary Function Test Laboratory Technician

- Pulmonary function test (PFT) technician will perform PFTs per local standard practice for pediatric patients

6 Visit schedule and assessments

The Core Phase will consist of two periods: a pre-randomization period consisting of screening and baseline visits, and a double-blind treatment period. The Extension Phase consists of a fingolimod treatment period.

The day of randomization in the Core Phase is defined as Day 1 of the study (Visit 3), which is the first day of study drug administration. Entry in the Extension Phase occurs at Visit 15 immediately following the completion of the Core Phase.

[Table 6-1](#), [Table 6-2](#) and [Table 6-3](#) lists all assessments and indicates with an “X” the visits when they are performed.

Patients should follow the visit schedule with an allowed visit window as follows:

- ± 2 days for Visit 4 and Visit 16
- ± 5 days for Visit 5 and all monthly visits
- ± 10 days for all quarterly and biannual visits
- + 14 days for Visit 15 (should be completed within 14 days of completion of Visit 14 / EOS-CP). Date of completion of Core Phase should be entered in the Study phase completion eCRF (date entered should be 1 day before Visit 15; first Extension Phase visit). Study drug should not be interrupted between the end of the Core Phase and the start of the Extension Phase.

Visit windows can be extended on a case-by-case basis to accommodate scheduling (please consult Sponsor for approval). The pre-randomization period may be extended with approval from the sponsor on a case by case basis to accommodate additional time needed to complete the screening assessments (e.g., additional lab tests, time to be (re)vaccinated, time to allow lab parameters to come within protocol requirements, etc.).

In addition to the scheduled visits, patients may have unscheduled visits following an onset of an MS relapse or for safety follow-up.

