9.5 Analysis of secondary variables

9.5.1 Key secondary variable(s)

Core Phase:

The key secondary variable is the annualized rate of the number of new/newly enlarged T2 lesions (n/neT2) from baseline to end of the study, with duration up to 24 months.

The null hypothesis for the key secondary analysis states that: there is no reduction in the neT2 lesion rate in patients treated with fingolimod 0.5 mg compared to patients treated with IFN β -1a, while the alternative hypothesis states there is a reduction in the neT2 lesion rate, in fingolimod 0.5 mg treated patients.

The test of the hypotheses will be based on a negative binomial regression model adjusted for treatment, pubertal status, number of T2 lesions at baseline and region. The natural log of (years in study for each patient) will be used as the offset.

For the key secondary analysis, there will be no imputations for missing data. The response variable for this analysis is the cumulative number of n/neT2 lesions based on the End of Study Core Phase MRI scan, for each patient. The quadratic variance estimate will be used and the natural log of time (in years) from randomization to the End of Study-Core Phase MRI assessment date for each patient will be used as the offset to account for the varying lengths of patients' time in study.

The above null hypothesis will be rejected if the observed p-value for treatment comparison (based on the n/neT2 rate ratio) is less than the significance level of 0.05. Model-based estimates of annualized rate of the number of n/neT2 lesions and their 95% confidence intervals, estimate of the n/neT2 annualized rate ratio (i.e., relative treatment effect) and its 95% confidence intervals and p-value for comparing fingolimod vs. IFN β -1a i.m. will be provided.

Summary statistics (mean, standard deviation, median, minimum and maximum) of the number of n/neT2 will also be provided.

Additional sensitivity analyses may be considered to further assess the robustness of the results.

Key efficacy variables data will be summarized for the overall population [REDACTED]

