3.8.2 Baseline

In general, a baseline value refers to the last measurement made prior to the administration of the first dose of the study drug. Assessments made on Day 1 may occur before or after the first dose. The following rules will be applied to determine which record is the last measurement prior to the first dose (i.e., the baseline value).

- Consider all records with an assessment date before the first dose date or with an assessment date on the same day of the first dose date and from Day 1 visit or before (i.e., visit\repeat visit number < 3). Baseline is the last record after sorting all above records with respect to assessment date, visit and repeat visit number.
- Some data specific rules for determining baseline will be applied as described below or in data specific sections if applicable.

For vital signs, the mean of the Day 1 pre-dose value will be used as baseline. If unavailable, the last available (including unscheduled) value before the first dose will be used.

For ECG, the Day 1 pre-dose value will be used as baseline. If unavailable, the last available (including unscheduled) value before the first dose will be used.

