4.2.2.4 MRI

MRI will be assessed at screening, Months 6, 12, 18, and 24 (end of study or early discontinuation) visits. Parameters collected at screening include: number and volume of T2 lesions, volume of T1 hypointense lesions, number and volume of Gd-enhancing lesions, and normalized brain volume. The following parameters will be collected at each post baseline visit:

- Number of new/newly enlarging T2 lesions (on each scheduled scan compared to previous scheduled scan and compared to the Screening scan)
- [REDACTED]
- Number of Gd-enhancing lesions (on each scheduled scan; optional for M18 scan)
- Volume of Gd-enhancing lesions (on each scheduled scan; optional for M18 scan)
- [REDACTED]
- [REDACTED]
- [REDACTED]
- [REDACTED]
- [REDACTED]

The number and volume of Gd-enhancing lesion data obtained less than 30 days after use of steroid for treatment of relapses will be excluded from the analysis.

The following is the complete list of the MRI endpoints, including the annualized rate of the number of new/newly enlarged T2 lesions (the designated key secondary endpoint) and the secondary endpoint of the number of T1 Gd-enhancing lesions per scan up to Month 24 (i.e., month 0 to EOS), which is also discussed in detail in [Section 4.2.2.2](#), as well as the exploratory endpoints. The time point of EOS is the last MRI scan in the core study. :

[figure not shown]
[figure not shown]
T2 lesions:

- Annualized rate of the number of new/newly enlarged T2 lesions up to Month 24 (i.e., Month 0 to EOS) and by visit (i.e., Month 0 to 6, Month 0 to 12, Month 0 to 18, and Month 0 to 24).
- Proportion of subjects free of new/newly enlarging T2 lesions up to Month 24 (Month 0 to EOS) and by visit (i.e., Month 0 to 6, Month 0 to 12, Month 0 to 18, and Month 0 to 24).

- [REDACTED]

Gd-enhancing lesions:

- Number of Gd-enhancing lesions per scan up to Month 24 (Month 0 to EOS) and number of Gd-enhancing lesions by visit (i.e., Month 6, Month 12, Month 18, and Month 24).
- Proportion of subjects free of Gd-enhancing lesions at EOS and by visit (i.e., Month 6, Month 12, Month 18, and Month 24).
- Volume of Gd-enhancing lesions at EOS and by visit (i.e., Month 6, Month 12, Month 18, and Month 24).

All MRI endpoints specified above will be summarized using descriptive statistics by treatment group and visit.

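### Key secondary endpoint: T2 lesions are counted from the Screening scan but the time offset starts at Day 1, so the reported annualised rates are overstated in both arms

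*SAP*

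**What the plan says.** **Count.** SAP 4.2.2.2 defines the endpoint from baseline to the end of the core phase. SAP 4.2.2.4 gives the schedule: "MRI will be assessed at screening, Months 6, 12, 18, and 24 (end of study or early discontinuation) visits". Each post-baseline scan is read for new or newly enlarging T2 lesions "on each scheduled scan compared to previous scheduled scan and compared to the Screening scan". SAP 3.8.2 says that, in general, "a baseline value refers to the last measurement made prior to the administration of the first dose of the study drug". With no Day 1 scan listed, the MRI baseline is the Screening scan. SAP 4.2.2.2.1 adds: "The response variable for this analysis is the cumulative number of n/neT2 lesions up to Month 24 (i.e., Month 0 to EOS), for each subject".

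**Offset.** SAP 4.2.2.2.1 uses the log of "time (in years) from first dose of study treatment to the last available T2 MRI assessment date". Protocol 9.5.1 runs it "from randomization to the End of Study-Core Phase MRI assessment date". Each of these sections also describes the offset more loosely as the time or years in study, and SAP Table 4-2 does the same. SAP 4.1.2 ends time in study at the final visit, not at a scan.

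**Gap.** Protocol Section 6 makes the day of randomization Day 1 and the first day of dosing. It also says: "The pre-randomization period may be extended with approval from the sponsor", case by case, with vaccination among the examples. Protocol Section 4 sets no minimum time in the Core Phase.

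**The concern.** A rate needs its numerator and denominator to cover the same interval. Here the count opens at the Screening scan and the clock opens at Day 1. The Month 0 label does not close this, because no scan is listed at Month 0. Adding up scan-to-scan counts does not close it either: the scan before the first post-baseline scan is the Screening scan.

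The gap cannot be zero by design. The Screening MRI feeds an exclusion criterion (protocol 4.2), and central review of the diagnosis must precede randomization (protocol 4.1). Protocol 15.6 asks for about a month between the last varicella or MMR dose and randomization, so a patient vaccinated during screening could have a longer gap, depending on when the scan was done.

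At stake are the model-based annualised rates and their 95% confidence intervals, which SAP 4.2.2.2.1 lists as outputs. Because follow-up is flexible, patients with little time in the Core Phase carry the largest relative error.

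**Working it through.** **1. Reproduce the plan's figure.** Inputs from protocol 9.7 and SAP 9.2: 95 per arm; 4.6 (interferon) and 2.3 (fingolimod) lesions over 24 months; dispersion k = 2.0 or 2.67. By protocol Appendix 5, Equation 2, Var = (1/n)[1/μ1 + 1/μ2 + 2k].

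- k = 2.0: (1/2.3 + 1/4.6 + 4.0)/95 = 0.0490; power = Φ(0.693/√0.0490 − 1.96) = 87.9%. Stated: about 88%.
- k = 2.67: power = 78.8%. Stated: about 79%.

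The planning rates per year are 4.6/2 = 2.3 and 2.3/2 = 1.15, ratio 0.50.

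**2. Expected reported rate.** Let λ be the on-study rate, λ0 the pre-dose rate, g the gap from Screening scan to first dose, and T the offset in years.

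Reported rate = (λT + λ0g)/T, so the overstatement is (λ0/λ)(g/T).

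If λ0 = λ this is g/T. If λ0 = 2.3 in both arms, it is g/T for interferon and 2g/T for fingolimod.

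**3. Assumptions.** The text available gives neither g nor λ0. I take g = 2, 4 and 8 weeks (0.038, 0.077 and 0.153 years), λ0 = 2.3 per year, and equal follow-up in the two arms.

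| Gap | T | Interferon | Fingolimod | Reported ratio (true 0.50) |
|---|---|---|---|---|
| 2 weeks | 2 y | +1.9% | +3.8% | 0.509 |
| 4 weeks | 2 y | +3.8% | +7.7% | 0.518 |
| 8 weeks | 2 y | +7.7% | +15.3% | 0.536 |
| 2 weeks | 1 y | +3.8% | +7.7% | 0.518 |
| 4 weeks | 1 y | +7.7% | +15.3% | 0.536 |
| 8 weeks | 1 y | +15.3% | +30.7% | 0.566 |
| 4 weeks | 0.5 y | +15.3% | +30.7% | 0.566 |

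Doubling λ0 doubles the overstatement. Planning power at T = 2 and k = 2.0 moves from 87.9% to 86.3%, 84.6% and 81.2% for gaps of 2, 4 and 8 weeks.

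**4. Effect of a scan-to-scan offset (4 weeks, T = 2).**

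- Interferon: (4.6 + 2.3 × 0.0767)/2 = 2.39 as planned; divided by 2.0767 it is 2.30 (true 2.30).
- Fingolimod: (2.3 + 2.3 × 0.0767)/2 = 1.24 as planned; divided by 2.0767 it is 1.19 (true 1.15).
- The ratio is 0.518 either way, because both denominators change by the same factor.

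**5. Unequal follow-up.** Assume 1.7 years on fingolimod and 1.4 on interferon.

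- No drug effect: ratio = [(1.7 + g)/1.7]/[(1.4 + g)/1.4] = 0.990, 0.981 and 0.974 for gaps of 30, 60 and 90 days. With SE = √0.0490 ≈ 0.22 on the log scale, the shift is 0.04 to 0.12 SE, and two-sided type I error is 5.02% to 5.17%.
- Planned effect: a true 0.50 is reported as 0.518, 0.534 and 0.548.

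**The case against.** The best defence is that a clock starting at first dose fits an objective about treated patients and matches the ARR clock in SAP 4.1.2. That would answer the point if the count started there too; it does not.

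Three further objections stand as limits.

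- The size is not fixed by the documents. Protocol Table 6-1 was not in the text available, extension of screening is by exception, and nothing says the MRI is done early in an extended period. That Screening is the only pre-dose scan rests on SAP 4.2.2.4.
- Where the looser time-in-study wording is followed and the final visit is later than the last scan, the longer denominator partly offsets the overstatement.
- A scan-to-scan offset does not repair the treatment estimate. Pre-dose lesions stay in the count. With the unequal follow-up in step 5 and a 30-day gap, the ratio at the planned effect would be 0.523 instead of 0.518.

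A reader might go further and infer that shorter interferon follow-up would tilt the comparison toward fingolimod. The documents do not support that. The gap precedes randomization, so it is balanced in expectation. The 1.7 and 1.4 years are illustrative and no section predicts such a difference; patients who stop drug are encouraged to stay, and their abbreviated schedule keeps the MRIs (protocol Section 6, Table 6-2). Even granting the difference, the tilt needs a true ratio above 1.4/1.7 = 0.82. At the planned effect the shift is toward 1.

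A reader might also see a conflict between randomization and first dose as start points. Both are Day 1 by protocol Section 6, so that difference is nominal.

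**Conclusion.** The point holds for the reported annualised rates and their confidence intervals. Both arms are overstated whenever the gap and the pre-dose lesion rate are above zero. With gaps of 2 to 8 weeks and a pre-dose rate of 2.3 per year, both assumed, the excess at 2 years is about 2–8% for interferon and 4–15% for fingolimod, rising as follow-up shortens.

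It does not hold as a challenge to the test. With balanced follow-up the null hypothesis is unaffected, and with the imbalance examined the effect is negligible. At the planned effect the ratio is mildly conservative, with a small loss of power. There is no meaningful bias toward fingolimod.

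**What to change.** In SAP 4.2.2.2.1, SAP Table 4-2 and protocol 9.5.1, use one offset: the natural log of years from the date of the Screening (baseline) MRI to the date of the last T2 MRI used in the count. Remove the time-in-study wording there. State that the rate includes lesions formed between the Screening scan and Day 1. The by-visit T2 rates in SAP Table 4-4 refer back to Table 4-2 and should follow the same definition.

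The cost is a wording change made before database lock; both scan dates are already collected. The downsides should be stated: the denominator takes in a short untreated period, the reported rates become slightly lower, and neither the pre-dose lesions nor the small dilution of the ratio is removed. Removing those would need a reference scan at or near Day 1, which the SAP's schedule does not list.

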4.2.2.3 Relapses

All relapse related analyses in this section will consider confirmed relapses only unless otherwise specified and will be conducted on the FAS.

4.2.2.3.1 Time to first relapse and proportion of relapse-free subjects

Time to first relapse and proportion of relapse-free subjects are considered as other secondary endpoints related to relapses.

For subjects with at least one event (i.e., relapse), time to event is calculated as (event start date – 1st core dose date + 1). For subjects without event, time to event will be calculated the same as the time in study for ARR in [Section 4.1.2](#).

The log-rank test of the treatment difference in the Kaplan–Meier estimates of the survival function of the time to first relapse will be performed.

Kaplan-Meier (KM) estimates of the survival functions will be constructed by treatment group. KM estimates of the relapse free patients at 12 and 24 months, together with 95% confidence intervals will be presented. Two-sided 95% confidence intervals of the difference in KM estimates will also be presented. The corresponding KM plot will be provided.

Cox’s proportional hazards model adjusted for treatment, region, pubertal status (the stratification factor in IVRS), and number of relapse within the previous two year before randomization will be performed as a supportive analysis. Estimates of the hazard ratio and its 95% confidence intervals, and the p-value for treatment comparison from the Cox model will be provided.

4.2.2.3.2 Relapse characteristics

The following relapse characteristics will be summarized at relapse level: severity (mild/moderate/severe), affecting daily activities (yes/no), steroid used (yes/no), hospitalization (yes/no), recovery status (none/partial/complete), and duration of relapse (days).

The following relapse characteristics will be summarized at patient level: severity, affecting daily activities, steroid used, hospitalization, and recovery status. For summaries at patient level, a patient is counted only in the most severe category for each variable.

Summaries of the above mentioned relapse characteristics will be performed for confirmed relapses and for all relapses (confirmed and unconfirmed) as well.

The proportion of subjects hospitalized for relapse and the proportion of subjects with severe relapses will be compared between treatment groups using a Chi-square test.

The severity of confirmed MS relapses will be derived according to the criteria in [Table 4-3](#). For severity derivation, the EDSS data obtained on the date of relapse confirmation (as collected on the Relapse eCRF page) will be used.

Table 4-3 Severity of MS relapse

Mild relapse	Moderate relapse	Severe relapse
EDSS increase of 0.5 point	EDSS increase of 1 or 2 points	Exceeding Moderate criteria
Or	Or	Or
1 point FS change in one to three systems	2-point FS change in one or two systems	Exceeding Moderate criteria
	Or	Or
	1-point change in four or more systems	Exceeding Moderate criteria

[Panitch et al 2002]

4.2.2.3.3 ARR in the first and second year

The ARR will be summarized for the following periods: 0 to 12 months and 13 to 24 months. The number of days on study for a specified period is calculated as follows:

- For 0 to 12 month summaries: (12 months cutoff date – first core dose date + 1).
- For 13 to 24 month summaries: (24 months cutoff date – 12 months cutoff date).

The 24 months cutoff date is the date corresponding to the last day of time in the core phase defined in [Section 4.1.2](#). If a subject completes the study or discontinues the study after Month 12 visit, the 12 months cutoff date will be the Month 12 visit date. If the Month 12

visit date (from the VIS data set) is not available, the 12 months cutoff date will be date corresponding to Day 360. If a subject discontinues or completes the study prior to Month 12 visit, he or she will only be included in the 0 to 12 month summaries and the 12 months cutoff date will be the date corresponding to the last day of time in study if time in study is less than 360 days or the date corresponding to Day 360 if otherwise.

4.2.2.3.4 Cumulative ARR by time

To further investigate the possible change in ARR over time, cumulative ARRs from Month 0 to the following time points will be estimated using the same NB model as for the primary analysis:

- Month 0 to Month 3 (including data up to 90 days)
- Month 0 to Month 6 (including data up to 180 days)
- Month 0 to Month 9 (including data up to 270 days)
- Month 0 to Month 12 (including data up to 360 days)
- Month 0 to Month 15 (including data up to 450 days)
- Month 0 to Month 18 (including data up to 540 days)
- Month 0 to Month 21 (including data up to 630 days)
- Month 0 to Month 24 (including data up to 720 days)

The estimated ARR (LSmean estimated with the OM option and 95% CI) by time and treatment will be plotted to allow for the detection of any trend of ARR over time within each treatment arm.

4.2.2.4 MRI

MRI will be assessed at screening, Months 6, 12, 18, and 24 (end of study or early discontinuation) visits. Parameters collected at screening include: number and volume of T2 lesions, volume of T1 hypointense lesions, number and volume of Gd-enhancing lesions, and normalized brain volume. The following parameters will be collected at each post baseline visit:

- Number of new/newly enlarging T2 lesions (on each scheduled scan compared to previous scheduled scan and compared to the Screening scan)
- [REDACTED]
- Number of Gd-enhancing lesions (on each scheduled scan; optional for M18 scan)
- Volume of Gd-enhancing lesions (on each scheduled scan; optional for M18 scan)
- [REDACTED]
- [REDACTED]
- [REDACTED]
- [REDACTED]
- [REDACTED]

The number and volume of Gd-enhancing lesion data obtained less than 30 days after use of steroid for treatment of relapses will be excluded from the analysis.

The following is the complete list of the MRI endpoints, including the annualized rate of the number of new/newly enlarged T2 lesions (the designated key secondary endpoint) and the secondary endpoint of the number of T1 Gd-enhancing lesions per scan up to Month 24 (i.e., month 0 to EOS), which is also discussed in detail in [Section 4.2.2.2](#), as well as the exploratory endpoints. The time point of EOS is the last MRI scan in the core study. :

[figure not shown]
[figure not shown]
T2 lesions:

- Annualized rate of the number of new/newly enlarged T2 lesions up to Month 24 (i.e., Month 0 to EOS) and by visit (i.e., Month 0 to 6, Month 0 to 12, Month 0 to 18, and Month 0 to 24).
- Proportion of subjects free of new/newly enlarging T2 lesions up to Month 24 (Month 0 to EOS) and by visit (i.e., Month 0 to 6, Month 0 to 12, Month 0 to 18, and Month 0 to 24).

- [REDACTED]

Gd-enhancing lesions:

- Number of Gd-enhancing lesions per scan up to Month 24 (Month 0 to EOS) and number of Gd-enhancing lesions by visit (i.e., Month 6, Month 12, Month 18, and Month 24).
- Proportion of subjects free of Gd-enhancing lesions at EOS and by visit (i.e., Month 6, Month 12, Month 18, and Month 24).
- Volume of Gd-enhancing lesions at EOS and by visit (i.e., Month 6, Month 12, Month 18, and Month 24).

All MRI endpoints specified above will be summarized using descriptive statistics by treatment group and visit.

The proportion type endpoints will be analyzed using the logistic regression model adjusted for treatment, region, pubertal status (the stratification factor in IVRS), and other covariates as applicable. The odds ratio and its 95% confidence intervals, and the p-value for treatment comparisons from the logistic regression model will be provided.

The count type endpoints (i.e., number of lesions) will be analyzed using the negative binomial regression model adjusted for treatment, region, pubertal status (the stratification factor in IVRS), and other covariates as applicable. The LSmean estimated with the OM option and their 95% confidence intervals, estimate of the rate ratio (i.e., relative treatment effect) and its 95% confidence intervals, and the p-value for treatment comparisons from the negative binomial regression model will be provided.

All other continuous endpoints will be analyzed using a rank ANCOVA model adjusted for treatment, region, and other covariates as applicable.

A parametric ANCOVA model with the same factors and covariates will be used for the endpoint of percent brain volume change and ARBA. The LSmean estimated with the OM option and its 95% confidence intervals, the estimate of between group difference and its 95% confidence interval, and the p-value for treatment comparisons from the ANCOVA model will be provided.

Table 4-4 lists the MRI endpoints and the analysis to be performed. Covariates to be included in the above mentioned statistical models are also specified in this table.

Table 4-4 MRI endpoints & analyses

Endpoint	Analysis model (covariates)
Annualized rate of the number of new/newly-enlarged T2 lesions by visit	As in Table 4-2. Response variable is the number of ne/newly-enlarged T2 lesions compared to baseline at the visit of interest
Number of Gd-enhancing lesions by visit	As in Table 4-2. Response variable is the number of Gd-enhancing lesions at the

[REDACTED]
	
visit of interest.
 
[REDACTED]

[REDACTED]
	
[REDACTED]

Proportion of subjects free of new/newly-enlarged T2 lesions compared to baseline by visit
	
Logistic regression (treatment, pubertal status (the stratification factor in IVRS), and region as factors, baseline no. of T2 lesions as covariate)


Proportion of subjects free of Gd-enhancing lesions by visit
	
Logistic regression (treatment, pubertal status (the stratification factor in IVRS), and region and factors, baseline no. of Gd-enhancing lesions as covariate)

[REDACTED]
	
[REDACTED]

Volume of Gd-enhancing lesions by visit
	
RANK ANCOVA (treatment, region, pubertal status (the stratification factor in IVRS), and baseline volume of Gd-enhancing lesions)

[REDACTED]
	
[REDACTED]

[REDACTED]
	
[REDACTED]

[figure not shown]
